Appendix H Statin Therapy

- atorvastatin 10 to 40 mg once daily
- rosuvastatin 2.5 to 20 mg once daily
- simvastatin 10 to 20 mg once daily
- pitavastatin 1 to 4 mg once daily
- fluvastatin 60 mg once daily

These statin therapies are selected by referring to moderate- or high-intensity statin therapy in the American College of Cardiology/American Heart Association (ACC/AHA) 2018 Guideline on the Management of Blood Cholesterol, and expected to lower LDL-C levels by $\geq 30\%$ in Japanese patients.

Appendix I Abbreviations

Abbreviation or special term	Explanation
ADA	Antidrug antibody
AE	Adverse event
ALP	Alkaline phosphatase
ALT	Alanine aminotransferase/transaminase
Apo	Apolipoproteins
aPTT	Activated partial thromboplastin time
ASO	Antisense oligonucleotide
AST	Aspartate aminotransferase/transaminase
BMI	Body mass index
BP	Blood pressure
bpm	Beats per minute
BUN	Blood urea nitrogen
CK	Creatine kinase
CSP	Clinical study protocol
CSR	Clinical study report
CVD	Cardiovascular disease
DBP	Diastolic blood pressure
DILI	Drug induced liver injury
DNA	Deoxyribonucleic acid
ECG	Electrocardiogram
eCRF	Electronic case report form
EDC	Electronic data capture
EDTA	Ethylenediaminetetraacetic acid
EDV	Early discontinuation visit
eGFR	Estimated glomerular filtration rate
FDA	United States Food and Drug Administration
FSH	Follicle-stimulating hormone
GCP	Good Clinical Practice
GGT	Gamma glutamyl transpeptidase
GLDH	Glutamate dehydrogenase
Hb	Haemoglobin
HbA1c	Haemoglobin A1c
HCT	Haematocrit

Abbreviation or special term	Explanation
HDL-C	High-density lipoprotein cholesterol
HIV	Human Immunodeficiency Virus
HL	Hy's Law
HMG-CoA	3 hydroxy 3 methyl glutarylcoenzyme A
HR	Heart rate
hs-CRP	High sensitivity C-reactive protein
IB	Investigator's Brochure
IATA	International Airline Transportation Association
ICF	Informed consent form
ICH	International Council for Harmonisation
IEC	Independent ethics committee
IMP	Investigational medicinal product
IRB	Institutional Review Board
IRT	Interactive response technology
ISR	Injection Site Reaction
iSMC	internal Safety Monitoring Committee
IUD	Intrauterine device
IXRS	Interactive Voice/Web Response System
LDL	Low-density lipoprotein
LDL C	Low-density lipoprotein cholesterol
LH	Luteinizing hormone
LLN	Lower limit of normal
Lp(a)	Lipoprotein(a)
MCHC	Mean corpuscular haemoglobin concentration
MCV	Mean corpuscular volume
PCSK9	Proprotein convertase subtilisin/kexin type 9
PEF	Peak expiratory flow
PD	Pharmacodynamic(s)
PHL	Potential Hy's Law
PI	Principal investigator
PK	Pharmacokinetic(s)
QTcF	Corrected QT interval by Fredericia
RBC	Red blood cell
RTSM	Randomization and trial supply management
SAE	Serious adverse event

Abbreviation or special term	Explanation
SBP	Systolic blood pressure
SC	Subcutaneous(ly)
SD	Standard deviation
SoA	Schedule of Activities
TBL	Total bilirubin
TC	Total cholesterol
UACR	Urine albumin to creatinine ratio
ULN	Upper limit of normal
UPCR	Urine protein to creatinine ratio
VLDL-C	Very-low-density lipoprotein cholesterol
WBC	White blood cell

CSR	Clinical Study Report
CV	Coefficient of variation
DBL	Database lock
ECG	Electrocardiogram
eCRF	Electronic case report form
eGFR	Estimated glomerular filtration rate
HLT	High level term
IPD	Important Protocol Deviation
LDL-C	Low density lipoprotein cholesterol
LLOQ	Lower limit of quantification
MedDRA	Medical dictionary for regulatory activities
PCSK9	Proprotein convertase subtilisin/kexin type-9
PD	Pharmacodynamics
PK	Pharmacokinetics
PR	PR interval
PT	Preferred term
QRS	QRS wave
QT	QT wave
QTcF	Corrected QT Interval using Fridericia's Formula
RR	Respiratory rate
SAE	Serious adverse event
SAP	Statistical Analysis Plan
SC	Subcutaneous

Abbreviation or Specialized Term	Definition
SD	Standard deviation
SOC	System organ class
TBL	Total bilirubin
TEAE	Treatment-emergent adverse event
UNS	Unscheduled
ULN	Upper limit of normal
WHO-DD	World Health Organisation drug dictionary

AMENDMENT HISTORY

CATEGORY Change refers to:	Date	Description of change	In line with CSP?	Rationale
N/A	27-Apr-2021	Initial approved SAP	N/A	N/A
Derivation of primary endpoint(s)	30-Jun-2021	4.2.1.4/ 1 st bullet: Any AE → All AE	Y(V1)	Change as the result of Mock Shell review.
Statistical analysis method for secondary endpoint(s)	30-Jun-2021	4.2.5.4: - summarized by dose level → summarized by analytes and timepoints - presented by dose level → presented by analytes and timepoints - Figures for the arithmetic mean (SD) concentration → remove "(SD)" - (SD only on the linear scale) → (SD on the linear scale and gSD on the semi-logarithmic scale)	Y(V1)	Change as the result of Mock Shell review.
Statistical analysis method for secondary endpoint(s)	30-Jun-2021	4.2.6.4/ L2: Safety Analysis Set → PD Analysis Set for lipid parameters	Y(V1)	Correction
Statistical analysis method for secondary endpoint(s)	30-Jun-2021	4.2.6.4/ L3: delete "alongside the individual value of the respective visit".	Y(V1)	Change as the result of Mock Shell review.
Statistical analysis method for secondary endpoint(s)	30-Jun-2021	4.2.6.4/ L6: 95% Cis → gSD	Y(V1)	Change as the result of Mock Shell review.
Statistical analysis method for secondary endpoint(s)	30-Jun-2021	4.2.7.4/ L2: Safety Analysis Set → PD Analysis Set	Y(V1)	Correction
Statistical analysis method for secondary endpoint(s)	30-Jun-2021	4.2.8.4/ L2: Safety Analysis Set → PD Analysis Set	Y(V1)	Correction
Statistical analysis method for secondary endpoint(s)	30-Jun-2021	4.2.8.4/ L3: delete "alongside the individual value of the respective visit".	Y(V1)	Change as the result of Mock Shell review.
Other	30-Jun-2021	4.1.7: - prior disease → past disease - concomitant disease → current disease	Y(V1)	Change as the result of Mock Shell review.

Other	30-Jun-2021	4.6.2.2: - All overdose data will be listed → All overdose data will not be listed	Y(V1)	Change as the result of Mock Shell review.
Other	30-Jun-2021	4.6.3.2: - Any recorded abnormalities will be presented in the listings. → Any recorded abnormalities will not be presented in the listings	Y(V1)	Change as the result of Mock Shell review.
Other	15-Sep-21	Updated the analysis visits windows to coincide with the visits in the CSP	Y	Change requested.
Data presentation	15-Sep-21	Included analysis of the composite measure	Y	Change requested
Other	26-Oct-21	Summarised the lab and anti-AZD8233 antibodies analysis visit windows in a separate table	Y	Change as a result of BDR1
Data presentation	26-Oct-21	Additional summary for the liver enzyme abnormalities	Y	Change as a result of BDR1.
Other	05-Nov-21	Added detail that pre-treatment phase can be up to 28 days prior to IP administration	Y	Change requested.
Other	05-Nov-21	Added that Part C will be summarised in a separate SAP.	Y	Change requested.
Statistical analysis method for secondary endpoint(s)	23-May-22 (post-DBL)	Updated derivation of LDL-C derived by the Friedewald or Martin/Hopkins formula and added the corresponding reference	Y	To replace missing values which were negative due to formula.
Other	01-Jun-22 (post-DBL)	RAC (AUD) and RAC (Cmax) added to list of PK parameters	Y	To be in line with the parameters collected during study.
Other	04-Jul-22 (post-DBL)	Analysis visit numbers updated in Tables 1-4	Y	Updated to be in line with the CSP.

1 INTRODUCTION

The purpose of this document is to give details for the statistical analysis of study D7790C00006 – Part A, supporting the clinical study report (CSR). Additional statistical analysis plans (SAP) will be created detailing the analysis of Part B and Part C of the study.

The reader is referred to the clinical study protocol (CSP) and the electronic case report form (eCRF) for details of study conduct and data collection. This SAP is based on Version 2.0 of the CSP dated 13 November 2020 and Version 2.0 of the eCRFs dated 18 January 2021.

2 CHANGES TO PROTOCOL PLANNED ANALYSES

The Enrolled Set will be used for the summary of subject disposition instead of the Safety Analysis Set.

3 DATA ANALYSIS CONSIDERATIONS

3.1 Timing of Analyses

A single analysis of all data from Part A will be conducted after database lock (DBL) and all results will be included in the CSR. DBL will occur after completion of all follow up visits, approximately 16 weeks after last administration of study intervention to the last ongoing subject.

3.2 Analysis Populations

3.2.1 Enrolled Set

All participants who signed the informed consent form. The Enrolled Set will be used to summarize patient disposition.

3.2.2 Randomly Assigned to Study Intervention

All participants who were randomized. Participants will be analyzed according to the treatment to which they were randomized.

3.2.3 Safety Analysis Set

All participants randomly assigned to study treatment who took at least one dose of AZD8233 or placebo and for whom any post-dose data are available. Participants will be analyzed according to the treatment which they actually received. If a participant received study intervention from the wrong kit for only part of the treatment duration and then switched to another, the associated treatment group for that participant would be the treatment group that participant was randomized to. The Safety Analysis Set will be used as the analysis set for all summaries for safety evaluation unless stated otherwise and for the analysis of the immunogenicity data.

3.2.4 Pharmacokinetic Analysis Set

The Pharmacokinetic (PK) Analysis Set will consist of all subjects in the Safety Analysis Set who received AZD8233 and who have evaluable PK data, with no important protocol deviations thought to impact on the analysis of the PK data.

The exclusion of any subjects or time points from the calculation of the PK parameters will be documented by the PK scientist, including the reasons for exclusion.

The available concentration data and PK parameter data for any subjects excluded from the PK analysis set will be listed only. Concentration data for subjects excluded from the PK analysis set will be presented in the individual figures of concentration versus time plots.

The PK Analysis Set will be used to summarize the PK data.

3.2.5 Pharmacodynamic Analysis Set

The Pharmacodynamic (PD) Analysis Set will consist of all patients who received AZD8233 or placebo, who have at least one baseline and one post-baseline measurement for either the level of PCSK9 in plasma or the level of LDL-C in plasma, and who have no important protocol deviations thought to impact on the analysis of the data.

The available PD data for any subjects excluded from the PD analysis set will be listed only, together with a flag indicating patients excluded from the PD analysis set. Only subjects or samples in the PD analysis set will be included in the descriptive summary tables.

The PD analysis set will be used to analyse the lipid parameters (PCSK9, LDL-C and other lipids).

3.3 General Considerations

There is no formal statistical hypothesis testing in this study. Safety and tolerability after multiple dosing of AZD8233 █ (or placebo) will be descriptively evaluated. The following principles will be followed throughout the study:

- Continuous variables will be summarized by the number of non-missing observations, mean, standard deviation (SD), median, first and third quartiles, and the minimum and maximum as appropriate.
- Log-transformed continuous variables will be summarized in a similar manner. In addition, the relative change from baseline will be calculated by back-transforming the change from baseline of the logarithmic variable as necessary.

- Categorical variables will be summarized as counts (n) and percentages (%). Unless otherwise stated, percentages will be calculated using the relevant analysis set population total as the denominator. Percentages will not be presented for zero counts.
- Mean and medians will be rounded to one additional decimal place relative to the original data, the SD will be rounded to two additional decimal places, and the maximum, minimum and quartiles will be displayed with the same accuracy as the original data. 95% confidence intervals (CIs) will be presented to one more decimal place than the raw data. Percentages (proportion) will be rounded to one decimal place.
- Summaries will be provided by time point of assessment where appropriate. Where summaries are over time, study day will be calculated in relation to the date of first dose of study treatment.
- Corresponding listings will be provided for all tabulated results unless stated otherwise. Any additional listings that are required will be described in the appropriate sections of the SAP.
- SAS® version 9.3 or higher will be used for all data analyses.

3.3.1 General Study Level Definitions

3.3.1.1 Definition of Baseline

Unless otherwise specified, ‘baseline’ refers to the last measurement obtained before the first dose of study intervention. For lipid parameters (PCSK9, LDL-C, etc), the geometric mean of the two measures taken pre-dose at Visit 2 (Day -1 and pre-dose Day 1) will be considered as baseline.

3.3.1.2 Handling of Missing Data

In general, missing data will not be imputed and will be treated as missing unless specifically described in an analysis section. The following considerations are made for missing safety data, adverse event (AE) dates, and concomitant medication/diseases dates:

- Safety assessment values of the form ‘<x’ or ‘>x’ (i.e., above or below the limits of quantifications) will be imputed as ‘x’ in the calculation of summary statistics but displayed as ‘<x’ or ‘>x’ in the listings.
- Adverse events that have missing causality after data querying will be assumed to be related to study drug.
- For missing AE/concomitant medication/disease start dates, the following will be applied:

- Missing day: Impute 1st of the month unless the month is the same as that of the first dose of study drug in which case impute first dose date.
- Missing day and month: Impute 1st January unless the year is the same as that of the first dose date in which case impute first dose date.
- Missing year: Impute the year of dosing.
- Completely missing: Impute first dose date unless the end date suggests it could have started prior to this in which case impute 1st January of the same year as the end date.
- For missing AE/concomitant medication/disease end dates, the following will be applied:
 - Missing day: Impute the last day of the month unless the month is the same as that of the last dose of the study drug in which case impute the date of last dose.
 - Missing day and month: Impute 31st December unless the year is the same as that of the last dose of study drug in which case impute date of last dose.
 - Missing year: Impute the year of dosing.
 - Completely missing: Do not impute a date i.e., assume that AE/concomitant medication/disease is ongoing.

For all missing start/end dates, flags will be retained in the analysis datasets indicating where any programmatic imputation has been applied, and in such cases, any durations would not be calculated.

If a subject is known to have died where only a partial death date is available, then the date of death will be imputed as the latest of the last known date to be alive + 1 from the database and the death date using the available information provided:

- Missing day only: Use the 1st of the month.
- Missing day and month: Use 1st January.
- Missing year: Impute the year of dosing.

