4.1.7 Medical History and Concomitant Disease

4.1.7.1 Definitions and Derivations

Medical and surgical history, and concomitant (called “current”) diseases are coded using MedDRA version 23.1 or higher. The imputation method described in Section 3.3.1.2 will be used in the instance that partial or missing dates are recorded. After imputation of dates, concomitant diseases will be classified as prior (called “past”) or current.

A past disease is defined as any disease with a start and end date prior to the first dose date (exclusive). A current disease is defined as any disease with an end date on or after the first dose date. A disease with a completely missing end date will be considered as current.

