4.1.8 Prior and Concomitant Medications

4.1.8.1 Definitions and Derivations

Prior and concomitant medications are coded using the WHO-DD. The imputation method described in Section 3.3.1.2 will be used in the instance that partial or missing dates are recorded.

Prior medications are defined as those that stopped and started prior to the first dose date. All medications on or after the first dose date are considered as concomitant, this includes those medications that started prior to date of first dose but continued after.

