4.2.1 Primary Endpoint – Adverse Events

4.2.1.1 Definition

An adverse event (AE) is the development of any untoward medical occurrence in a patient or clinical study participant administered a medicinal product and which does not necessarily have a causal relationship with this treatment. An AE can therefore be any unfavourable and unintended sign (eg, an abnormal laboratory finding), symptom (for example nausea, chest pain), or disease temporally associated with the use of a medicinal product, whether or not considered related to the medicinal product.

The term AE is used to include both serious (SAE) and non-serious AEs and can include a deterioration of a pre-existing medical occurrence. An AE may occur at any time, including run-in or washout periods, even if no study intervention has been administered.

A treatment-emergent adverse event (TEAE) is defined as an AE with an onset date on or after the first dose date.

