4.2.1.4 Primary Analysis of Primary Endpoint

All summaries of adverse event data will be based on the Safety Analysis Set and will be presented by treatment group. Summary tables will include TEAEs only whereas listings will include all reported AEs.

A subject-level overview of AEs (the number and percent of subjects and the number of events) will be tabulated in a single table for:

- All AE.
- AEs possibly related to study treatment.
- AEs with an outcome of death.
- AEs with outcome of death possibly related to study treatment.
- All serious adverse events (SAE).
- SAEs possibly related to study treatment.
- AEs leading to discontinuation of study treatment.
- AEs leading to discontinuation of study treatment, possibly related to study treatment.
- AEs leading to dose interruption and reduction (separately).
- AEs leading to withdrawal from the study.

Separate AE summary tables of the number and percentage of subjects with AEs and the number of events in each of the categories above will be produced by SOC and PT.

Additionally, the following tables will be presented by SOC and PT:

- AEs by the maximum reported intensity.
- AEs by causality assessment.

Subjects with multiple events in the same category are counted once in that category. Subjects with events in more than one category are counted once in each of those categories.

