3.3.1.2 Handling of Missing Data

In general, missing data will not be imputed and will be treated as missing unless specifically described in an analysis section. The following considerations are made for missing safety data, adverse event (AE) dates, and concomitant medication/diseases dates:

- Safety assessment values of the form ‘<x’ or ‘>x’ (i.e., above or below the limits of quantifications) will be imputed as ‘x’ divided by the square root of 2 in the calculation of summary statistics but displayed as ‘<x’ or ‘>x’ in the listings.
- AEs that have missing causality after data querying will be assumed to be related to study drug.
- For missing AE start dates, the following will be applied:
 - Only partial AE start dates are imputed. Dates which are completely missing are not imputed.
 - If only the day is missing and the month and/or the year is different from the month and year of the first dose of investigational product (IP), assume 01-MMM-YYYY. If the month and year are the same as the first dose of IP month and year and the end date is on or after (including ongoing / missing) the first dose of IP, then assume the date of the first dose of IP. If the month and year are the same as the first dose of IP month and year and the end date is prior to the first dose of IP, then assume the end date.

- If the month is missing and the year is different from the year of first dose of IP, assume 01-JAN-YYYY of the collected year. If the year is the same as the first dose of IP year and the end date is on or after (including ongoing / missing) the first dose of IP, then assume the date of the first dose of IP. If the year is the same as the first dose of IP and the end date is prior to the first dose of IP, then assume the end date.
- After applying these rules, if the imputed AE start date is after a complete AE end date then assume the same date as the complete AE end date; if the end date is missing and the imputed AE start date is after the end of study date then assume the same date as the study end date.
- For missing AE end dates, the following will be applied:
 - Completely missing AE end dates are not imputed.
 - If the AE is ongoing, the end date is set to missing.
 - If the AE is not ongoing, and if only the day is missing then assume the last day of the collected month.
 - If the AE is not ongoing, and both, the day and the month are missing then assume 31-DEC of the collected year.

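### SAP Parts A and C impute the first dose date for some partial start dates without checking a recorded earlier end date, so a record that ended before dosing can be classed as on-study

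*SAP*

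**What the plan says.** SAP Part A section 3.3.1.2 has one set of start-date rules for adverse events, medications and diseases.

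- Day missing: the first of the month, "unless the month is the same as that of the first dose of study drug in which case impute first dose date".
- Day and month missing: "Impute 1st January unless the year is the same as that of the first dose date in which case impute first dose date".
- Start completely missing: "Impute first dose date unless the end date suggests it could have started prior to this", in which case 1 January of the end-date year is used.

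Only the third rule consults the end date. No later sentence in the section compares an imputed start with a known end. The section keeps flags for imputed dates and does not calculate durations from them. SAP Part C section 3.3.1.2 repeats these rules and adds only a check against future dates.

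The classes that depend on these dates in SAP Part A are:

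- Section 4.2.1.1: a treatment-emergent event "is defined as an AE with an onset date on or after the first dose date". Section 4.2.1.4 adds: "Summary tables will include TEAEs only whereas listings will include all reported AEs".
- Section 4.1.8.1: "Prior medications are defined as those that stopped and started prior to the first dose date". Medications from first dose onward are concomitant.
- Section 4.1.7.1: "A past disease is defined as any disease with a start and end date prior to the first dose date". A disease is current if its end is on or after first dose. The classes are assigned after imputation.

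SAP Part C has the same event and medication definitions, but its section 4.1.7.1 defines no past class for diseases.

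SAP Part B section 3.3.1.2 treats the case differently for adverse event starts. When the known month or year matches first dose and "the end date is prior to the first dose of IP, then assume the end date". It then adds a general check that an imputed start does not fall after a complete end date. It imputes no medication start dates at all.

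**The concern.** Giving an uncertain onset the first dose date is a reasonable conservative default when the record could have begun on treatment. It is not reasonable when the recorded end date shows that the record was over before dosing. The rule then creates a start later than the end, and the downstream definitions act on that start.

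The rule also works against its neighbour in the same section. If nothing is known about the start, the end date is used and the record is placed before dosing. If the year is known and matches the dosing year, the end date is ignored and the record is placed on the first dose date. More information gives the worse answer, which points to an omission and not to a design choice.

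What is at stake is whether the descriptive tables and listings show pre-dose medications, diseases and, occasionally, a serious event in the right class.

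**Working it through.** No figure in the plan is to be reproduced. The check applies the written rules to records with a known end date before first dose.

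**Inputs.** Start-date rules: SAP Part A section 3.3.1.2. Classes: SAP Part A sections 4.2.1.1, 4.1.8.1 and 4.1.7.1. Comparison rule: SAP Part B section 3.3.1.2. I read a matching month as the same month and year. The example dates are assumptions, with first dose on 20 Mar 2021.

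| Case | Recorded start | Recorded end | Imputed start | If a serious event | If a medication | If a disease |
|---|---|---|---|---|---|---|
| 1 | Mar 2021, no day | 10 Mar 2021 | 20 Mar 2021 | treatment-emergent | not prior; concomitant by imputed start | neither past nor current |
| 2 | 2021 only | 10 Feb 2021 | 20 Mar 2021 | treatment-emergent | not prior; concomitant by imputed start | neither past nor current |
| 3 | Feb 2021, no day | 10 Mar 2021 | 1 Feb 2021 | not treatment-emergent | prior | past |
| 4 | 2020 only | 10 Feb 2021 | 1 Jan 2020 | not treatment-emergent | prior | past |
| 5 | completely missing | 10 Feb 2021 | 1 Jan 2021 | not treatment-emergent | prior | past |

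Cases 1 and 2 are wrong: the imputed start is 10 and 38 days after the recorded end. Cases 3 to 5 are right, so the fault is confined to partial starts whose known month or year matches first dose.

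**With an end-date condition.** If the start is set to the end date whenever that date precedes first dose, cases 1 and 2 become 10 Mar and 10 Feb 2021. They are then not treatment-emergent, prior, and past.

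**Does it depend on the chosen dates?** Take every first dose date in 2021, every earlier end date in 2021, and only the start year known. That is 365 × 364 / 2 = 66,430 pairs. Under the SAP Part A rule 66,430 of 66,430 are misclassified; with the condition, 0. This shows that the rule fails for every such pair. It says nothing about how often such records occur.

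**Part C.** The event and medication columns are the same. The disease column does not apply, because current status there depends on the end date alone.

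**Which records can arise.** Protocol section 8.3.1 collects non-serious events only from first dose and serious events from consent, so the event column needs a serious event in screening. Protocol section 6.5 asks for medications being taken at enrolment or later. The typical medication case is therefore one stopped during the screening period of up to 28 days, as in case 1. Case 2 is more natural for a disease in the medical history.

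**Size per participant.** With the planned 8:3 allocation, 1/8 = 12.5% on AZD8233 and 1/3 = 33.3% on placebo.

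**The case against.** The strongest reply is that the consequences are small, and much of it stands.

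- *Adverse events.* A reader might infer that the primary safety tables of Parts A and C are materially distorted. The documents do not support that. The route needs a serious event in screening with an incomplete start date, although protocol section 8.3.2 collects start and stop times and hospitalisation dates. It also needs a known end before dosing, in someone still randomised despite exclusion criterion 24 on important illness within 4 weeks of first dose. For non-serious events the first dose date is a sound default.
- *Diseases.* A reader might infer that diseases drop out of reported tables. SAP Part A section 4.1.7.2 summarises medical history and current diseases and names no separate past-disease table, so no loss from a planned output is shown. Current status is right whatever start is imputed. The gap is one of definition, in Part A only.
- *Medications.* Failing the prior definition is certain. Concomitant follows from the imputed start. Someone who gave weight to the recorded stop could decline that label, but the drug would then be in neither class.
- *Excluded drugs.* A reader might infer that pre-study use would be counted as a protocol deviation. Deviations go through the Non-compliance Handling Plan and the Data Review Meeting (SAP Part A sections 3.3.5 and 4.1.3.1), and nothing says that imputed dates drive those decisions.
- *End dates.* The end-date rule can place an imputed end before the start of a record that began in follow-up. That date is impossible, but it changes no event, medication or disease class, and durations are not calculated.
- *SAP Part B as precedent.* It supports the condition for adverse event starts only.

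None of this defends the rule itself. The retained flags show that a date was imputed; they do not correct the class. For events, SAP Part A section 3.3.1.3 also assigns study periods after imputation, so the listing would show the wrong period too.

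**Conclusion.** The point holds as a fault in a stated rule with modest consequences. In SAP Parts A and C, a start whose known month or year matches first dose is set to the first dose date even when the recorded end date is earlier. Every record of that pattern gets an impossible start. The realistic effect is on the descriptive medication table in both parts and on disease classification in Part A. A change in an adverse event rate is possible but unlikely. Frequency is unknown, no formal inference is involved, and the 12.5 and 33.3 point shifts describe one affected participant, most often in a medication row.

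This rests on reading a matching month as the same month and year, and on applying the medication definitions to the imputed start. For Part A diseases the SAP says explicitly that classification follows imputation.

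**What to change.** In section 3.3.1.2 of SAP Parts A and C, make both partial-start rules conditional. Impute the first dose date only when the end date is on or after first dose, ongoing or missing. If the known end date is before first dose, set the start to the end date. Apply this to adverse events, medications and diseases alike. SAP Part B has the equivalent for adverse event starts; for medications and diseases it is an extension.

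As an optional tidy-up, add a check that no imputed end date precedes the start date. This changes no classification.

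The cost is a sentence or two in each SAP and a small program change. SAP Part A's amendment history already records changes made after database lock, so a documented correction is feasible. A listing of records whose imputed start falls after the recorded end would show at once whether any are affected.
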